6.1 Demographics and Baseline Characteristics

Demographic and baseline characteristics information will be collected at the Baseline visit of the study and will be summarized for the FAS. The number of observations, mean, standard deviation, median, minimum and maximum will be summarized for continuous variables. Categorical or discrete variables will be summarized via frequencies and percentages. Summary statistics will be computed for each treatment group and overall.

Main Demographic and Baseline Characteristics

- Sex (male/female)
- Age (years)
- Age Categories (< 40, [40, 65], \geq 65 years)
- Race (White, Black or African American, American Indian or Alaska Native, Native Hawaiian or Other Pacific Islander, Asian, Other)
- Country (China, South Korea, Brazil)
- Ethnicity (Hispanic or Latino, Not Hispanic or Latino)
- Weight (kg)
- Weight Categories (< 60 kg, \geq 60 kg)
- Height (cm)
- Body Mass Index (BMI) (kg/m²)
- Body Mass Index (BMI) Category (kg/m²) (BMI < 25 vs BMI \geq 25)

RA Medical History and Characteristics

- Duration of RA Symptoms in years
- Duration of RA Diagnosis in years
- Duration of RA Symptoms Categories (< 5 year or \geq 5 year)

- Duration of RA Diagnosis Categories (< 5 year or \geq 5 year)
- Prior exposure to bDMARDs (Yes or No)

ACR and/or DAS Components at Baseline

- Tender joint count (TJC68) defined as the number of tender joints out of 68 assessed joints
- Swollen joint count (SJC66) defined as the number of swollen joints out of 66 assessed joints
- Tender joint count (TJC28) defined as the number of tender joints out of 28 assessed joints used for DAS28 calculation
- Swollen joint count (SJC28) defined as the number of swollen joints out of 28 assessed joints used for DAS28 calculation
- Physician's global assessment of disease activity (mm on a 100-mm horizontal visual analogue scale [VAS])
- Patient's assessment of pain within last week (mm on a 100-mm horizontal (VAS))
- Patient's global assessment of disease activity within last 24 hours (mm on a 100-mm horizontal VAS)
- Health Assessment Questionnaire Disability Index of the (HAQ – DI) (range: 0 to 3)
- High sensitivity C-reactive protein (hsCRP) (mg/L)
- Erythrocyte sedimentation rate (ESR) (mm/hr)

Other Baseline RA Disease Characteristics

- Anti-cyclic citrullinated peptide (Anti-CCP) (units)
- Anti-CCP status: Positive or Negative
- Rheumatoid Factor (RF) (units)
- Rheumatoid Factor (RF) status: Positive or Negative
- RF and Anti-CCP both positive vs. at least one negative
- RF and Anti-CCP both negative vs. at least one positive

- Percentage of subjects on oral steroid at baseline
- Oral steroid dose (prednisone equivalent) at baseline
- MTX dose at baseline
- Concomitant csDMARD at baseline (MTX alone, MTX and other csDMARD, csDMARD other than MTX)
- DAS28 [hsCRP]
- DAS28 [ESR]
- DAS28 Categories:
 - DAS28 > 5.1 (High Disease Activity)
 - DAS28 ≤ 5.1
- Clinical Disease Activity Index (CDAI)
- CDAI categories:
 - CDAI > 22 (High Disease Activity)
 - CDAI ≤ 22
- Simplified Disease Activity Index (SDAI)
- SDAI categories:
 - SDAI > 26 (High Disease Activity)
 - SDAI ≤ 26

Patient Report Outcomes at Baseline

- Morning stiffness (severity and duration)
- Functional Assessment of Chronic Illness Therapy-Fatigue (FACIT-F)
- Work Instability Scale for Rheumatoid Arthritis (RA-WIS)
- 36-Item Short Form Health Survey (SF-36) Version 2: physical component summary, mental component summary and the 8 sub-domain scores
- EQ-5D-5L

Clinical Tests at Screening

- Chest x-ray

- ECG
- Tuberculin PPD skin test, QuantiFERON TB Gold test
- Hepatitis Testing
- Serum pregnancy test

Immunization History

- BCG immunization
- Herpes Zoster immunization
- Hepatitis B immunization

Tobacco/Nicotine and Alcohol Use

- Tobacco/Nicotine Use [user, ex-user, non-user, unknown]
- Alcohol Use [drinker, ex-drinker, non-drinker, unknown]

6.2 Medical History

Medical history data will be summarized and presented for FAS population using body systems and conditions/diagnoses as captured on the CRF. The body systems will be presented in alphabetical order and the conditions/diagnoses will be presented in alphabetical order within each body system. The number and percentage of subjects with a particular condition/diagnosis will be summarized for each randomized treatment group as well as overall. Subjects reporting more than one condition/diagnosis within a body system will be counted only once for that body system. No statistical comparison will be performed for medical history reporting.

6.3 Prior Treatment and Concomitant Medications

Prior and concomitant medications will be summarized by each randomized treatment group as well as overall for FAS. Prior medications are those medications taken prior to the first dose of study drug. This includes medications with a start date before the first study drug administration date, regardless of the end date of these medications.

Medications taken on the day of the first dose of study drug are not counted as prior medications. Concomitant medications are those medications, other than study drug, taken after the first dose of study drug and within 1 day of the last dose of study drug. This includes medications with a start date between first study drug administration and last study drug administration + 1 day, as well as, medications with a start date prior to first dose of study drug and which are ongoing after first dose of study drug. Medications taken on the day of the first dose of study drug are counted as concomitant medications.

The number and percentage of subjects who received a prior medication and the number and percentage of subjects who received a concomitant medication will be tabulated separately by the generic name assigned by the most current version of the World Health Organization (WHO) Drug Dictionary.

6.4 Protocol Deviations

Protocol deviations are categorized as follows based on ICH deviation criteria:

- Those who entered the study even though they did not satisfy the entry criteria
- Those who developed withdrawal criteria during the study and were not withdrawn
- Those who received the wrong treatment or incorrect dose, and
- Those who received an excluded or prohibited concomitant medication.

The protocol deviations listed above will be summarized and listed by treatment group.

7.0 Patient Disposition

The following will be summarized by randomized treatment group as well as overall:

- number of subjects randomized,
- number of subjects included in key analysis populations (Full Analysis Set and Per Protocol Analysis Set for primary efficacy analysis, Safety Analysis Set for Period 1),
- number of subjects who completed Period 1 study participation,

- number of subjects who entered Period 2,
- number of subjects on-going in Period 2 (if applicable),
- number of subjects who completed overall study (Period 1 and Period 2) participation.

This summary will be repeated by site.

Premature discontinuation details will be further summarized separately for Period 1 and Period 2 as follows.

Period 1

The number and percentage of subjects completed Period 1 and prematurely discontinued in Period 1 will be summarized by randomized treatment group, by study drug completion/discontinuation, with the primary reason for discontinuation collected from CRF by the following categories:

- Adverse event (AE)
- Withdrew consent
- Lost to follow-up
- Lack of efficacy
- Other.

Subjects may have more than one reason for discontinuing, but only the primary reason will be summarized.

In addition, the number and percentage of subjects enrolled in Period 2 will also be summarized by randomized treatment group.

Period 2

Period 2 patient dispositions and reason for discontinuation will be summarized for upadacitinib 15 mg QD group.

Among the subjects who entered Period 2, the number and percentage of subjects completed, on-going (if applicable), and prematurely discontinued study drug in Period 2 will be summarized.

For subjects who prematurely discontinued study drug, the primary reason for discontinuation will be summarized with the same categories as given above for Period 1.

Subjects may have more than one reason for discontinuing, but only the primary reason will be summarized.

8.0 Study Drug Exposure and Compliance

8.1 Study Drug Exposure

The duration of exposure to study drug will be summarized for the safety analysis set by the following groups.

1. Upadacitinib 15 mg QD

This includes upadacitinib 15 mg QD exposure from subjects starting on upadacitinib 15 mg QD and subjects switching from placebo to upadacitinib 15 mg QD.

2. Placebo

The duration of exposure to study drug will be summarized for each group as specified above, with the number of subjects, mean, standard deviation, median, minimum and maximum values. In addition, the number and percentage of subjects exposed to study drug will be summarized for the following cumulative duration intervals.

- ≥ 2 weeks
- ≥ 1 month
- ≥ 3 months
- ≥ 6 months

- ≥ 9 months
- ≥ 12 months

8.2 Compliance

Study drug compliance will be summarized for each treatment group for Period 1. The compliance is defined as the number of tablets taken (i.e., the difference between the number of tablets dispensed and the number of tablets returned) during the subject's participation in Period 1 divided by the number of days that the subject was in the Treatment Phase of Period 1.

9.0 Efficacy Analysis

9.1 General Considerations

There are two sets of planned efficacy analysis: efficacy analysis for Period 1 and long-term efficacy analysis. All efficacy analyses will be carried out using the FAS population.

9.1.1 Efficacy Analysis at Different Phases of the Study

Efficacy Analysis for Period 1

Standard efficacy analysis by randomized treatment groups (upadacitinib 15 mg QD and the placebo group) will be performed on efficacy data for Period 1 (up to Week 12). No protocol-defined treatment switching will occur prior to the time point. Formal statistical inference will be generated, and results from this set of analysis will be used as the key efficacy findings of this study.

Long-Term Efficacy Analysis

Long-term efficacy analysis will be performed on As Observed data (defined in Section 9.1.2) by randomized treatment group sequence as described below:

1. Upadacitinib 15 mg QD
2. Placebo → upadacitinib 15 mg QD.

There will be no statistical testing; only descriptive statistics and confidence intervals will be provided.

9.1.2 Definition of Missing Data Imputation

Non-Responder Imputation (NRI) Approach

The NRI approach will categorize any subject who has missing value for categorical variables at a specific visit as non-responder for that visit. In addition, subjects who prematurely discontinue from study drug will be considered as non-responders for all subsequent visits after discontinuation.

Observed Cases (OC)

The OC analysis will not impute values for missing evaluations, and thus a subject who does not have an evaluation on a scheduled visit will be excluded from the OC analysis for that visit. In addition, the OC will not use values after premature discontinuation of study drug. This sensitivity analysis will only be applied to the analysis in Period 1.

As Observed (AO)

The AO analysis will not impute values for missing evaluations, and thus a subject who does not have an evaluation on a scheduled visit will be excluded from the AO analysis for that visit. Regardless of treatment switching or premature discontinuation of study drug, all observed data will be used in the analysis. The AO analysis will be applied to long-term efficacy analysis.

Mixed Effect Model Repeat Measurement (MMRM)

The repeated measure analysis will be conducted using mixed model including observed measurements at all visits. The mixed model includes the categorical fixed effects of treatment, visit and treatment-by-visit interaction, main stratification factors at randomization, and the continuous fixed covariates of baseline measurement. An unstructured variance covariance matrix will be used. The parameter estimations are based on the assumption of data being missing at random and using the method of restrictive maximum likelihood (REML). The missing at random assumption is considered reasonable given the high placebo response rate typically seen in RA trials. Additionally, in RA trials, the proportion of discontinuation is relatively small (10 – 15% only) and the rate of discontinuation due to lack of efficacy is generally low (< 5%).

Multiple Imputation (MI)

The MI analysis will impute missing data multiple times under appropriate random variation and thus generate multiple imputed "pseudo-complete" datasets. Results will be aggregated across the multiple imputed datasets, overcoming drawbacks of the single imputation methods. PROC MI will be used to generate 5 datasets using the fully conditional specification (FCS) method. Specifically, treatment group is included in the FCS imputation model to enable sampling stratified by treatment groups. Additionally, the imputation model includes demographics variables and baseline disease characteristics, as well as longitudinal response observed at any other visits. An ANCOVA model will first be performed on each of the multiple imputed datasets adjusting for treatment, stratification factor and baseline value. PROC MIANALYZE will then be used to aggregate the results for the final statistical inference using Rubin's method. The imputation is based on assumption of data being missing at random. The missing at random assumption is considered reasonable given the high placebo response rate typically seen in RA trials. Additionally, in RA trials, the proportion of discontinuation is relatively small (10 – 15% only) and the rate of discontinuation due to lack of efficacy is generally low (< 5%).

9.2 Efficacy Analysis for Period 1

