**Methodology:**

This is a Phase 3 multicenter study that includes two periods. Period 1 is a 12-week, randomized, double-blind, parallel-group, placebo-controlled period designed to compare the safety and efficacy of upadacitinib versus placebo for the treatment of signs and symptoms of subjects with moderately to severely active RA who are on a stable dose of csDMARDs and have an inadequate response to csDMARDs. Period 2 is an open-label 52 week extension period to evaluate the long-term safety, tolerability, and efficacy of upadacitinib in subjects with RA who have completed Period 1.

The study duration will include a 35-day screening period; a 12-week randomized, double-blind, parallel group, placebo controlled treatment period (Period 1); an open-label 52 week extension period; and a 30-day follow-up period.

Subjects who meet eligibility criteria will be randomized in a 1:1 ratio to one of two treatment groups. As indicated below, it is expected that approximately 222 subjects will enter the study from China and 100 subjects from other countries including Brazil and South Korea:

- Group 1: Upadacitinib 15 mg QD (N = 161; 111 from China) (Period 1) → Upadacitinib 15 mg QD (Period 2)
- Group 2: Placebo (N = 161; 111 from China) (Period 1) → Upadacitinib 15 mg QD (Period 2)

Randomization will be stratified by country and the Chinese population will be up to 80% of the total study population.

Subjects must have been on a stable dose of csDMARD(s) for  $\geq$  4 weeks prior to the first dose of study drug and must remain on a stable dose until Week 24; the csDMARD dose may be decreased only for safety reasons.

Subjects with prior exposure to at most one biologic disease-modifying anti-rheumatic drug (bDMARD) for RA may be enrolled in the study (up to 20% of total number of subjects) after the required washout period is satisfied and if they have limited exposure (< 3 months) OR response to bDMARD but had to discontinue that bDMARD due to intolerance (regardless of treatment duration). Subjects who are considered bDMARD inadequate responders (lack of efficacy), as determined by the Investigator, are not eligible.

At Week 24, if a subject fails to meet the Low Disease Activity (LDA) criterion (LDA defined as CDAI  $\leq$  10), the investigator should adjust the subject's background RA therapies after assessments for Week 24 have been completed.

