Starting at Week 24 (after Week 24 assessments have been performed), initiation of or change in corticosteroids, non-steroidal anti-inflammatory drugs (NSAIDs), acetaminophen/paracetamol, low potency analgesics, or csDMARDs (restricted to oral or parenteral MTX, sulfasalazine, hydroxychloroquine, chloroquine and leflunomide, and restricted to concomitant use of up to 2 csDMARDs except the combination of MTX and leflunomide) is allowed as per local label. For RA flare treatment, no more than 3 consecutive days of systemic corticosteroids (maximum dose of 0.5 mg/kg/day of prednisone or its equivalent) is allowed, after which subject should resume their usual daily oral corticosteroid dose.

Subjects taking MTX should take oral folic acid throughout study participation. Folic acid dosing and timing of regimen will be based on the Investigator's discretion.

Starting at Week 24, at least 20% improvement in BOTH TJC AND SJC compared to baseline is required to remain on study drug. Anyone who does not fulfill this criterion at 2 consecutive visits (starting at Week 24) (see Section 5.2.3.1) must be discontinued from the study.

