At Week 24 (after Week 24 assessments have been performed) if a subject fails to meet the LDA criterion (LDA defined as CDAI  $\leq$  10), the investigator should adjust the subject's background RA therapies. Initiation of or change in corticosteroids, NSAIDs, acetaminophen/paracetamol, low potency analgesics, or csDMARDs (restricted to oral or parenteral MTX, sulfasalazine, hydroxychloroquine, chloroquine and leflunomide, and restricted to concomitant use of up to 2 csDMARDs except the combination of MTX and leflunomide) is allowed as per local label.

Starting at Week 24 (after Week 24 assessments have been performed) and thereafter, intra-articular, intramuscular, intravenous, trigger point or tender point, intra bursa, and intra-tendon sheath injections of corticosteroids, dosage and frequency per standard of

care, are allowed. However, joint injections should be avoided within 21 days prior to the next scheduled study visit to avoid confounding effects of systemic absorption of intra-articular corticosteroids. For the analysis of the TJC and SJC, injected joints will be considered "not assessable" for 3 months from the time of the intra-articular injection. For RA flare treatment, no more than 3 consecutive days of high-dose systemic corticosteroids (maximum dose of 0.5 mg/kg/day of prednisone or its equivalent) is allowed, after which subject should resume their usual daily oral corticosteroid dose.

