4.0 Study Objectives, Design and Procedures

4.1 Study Objectives

Period 1

1. To compare the efficacy of upadacitinib 15 mg QD versus placebo for the treatment of signs and symptoms of subjects with moderately to severely active RA who are on a stable dose of csDMARDs and have an inadequate response to csDMARDs.
2. To compare the safety and tolerability of upadacitinib 15 mg QD versus placebo in subjects with moderately to severely active RA who are on a stable dose of csDMARDs and have an inadequate response to csDMARDs.

Period 2

To evaluate the long-term safety, tolerability, and efficacy of upadacitinib 15 mg QD in subjects with RA who have completed Period 1.

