9.3 Long-Term Efficacy Analysis

Assessments to evaluate long-term efficacy will be analyzed for the following measures at Weeks 1, 2, 4, 8, 12, 16, 20, 24, 36, 48, and 64/PD:

- ACR20/50/70 response rates;
- Change from baseline in individual ACR components;
- Change from baseline in DAS28 (CRP);
- Change from baseline in DAS28 (ESR);
- Change from baseline in CDAI and SDAI;
- Change from baseline in morning stiffness;
- Proportion of subjects achieving change from baseline in HAQ-DI ≤ -0.22 for subjects with baseline HAQ-DI ≥ 0.22 ;
- Proportion of subjects achieving change from baseline in HAQ-DI ≤ -0.3 for subjects with baseline HAQ-DI ≥ 0.3 ;

- Proportion of subjects achieving LDA and proportion of subjects achieving CR based on DAS28 (CRP), DAS28 (ESR), SDAI, and CDAI criteria;
- Boolean remission;
- Proportion of subjects with no concomitant corticosteroid use (among subjects with corticosteroid use at baseline).

Assessments to evaluate long-term efficacy will be analyzed for the following measures at Weeks 4, 12, 24, 48:

- Change from baseline in EQ-5D-5L;
- Change from baseline in SF-36;
- Change from baseline in FACIT-F;
- Change from baseline in RA-WIS.

Descriptive statistics will be provided for each randomized treatment group sequence as defined in Section 9.1.1. These include the number of observations, mean, standard deviation, 95% CI, median, minimum, Q1, Q3 and maximum for continuous endpoints; and frequencies and percentages with 95% CI using normal approximation for binary endpoints. Plot for each randomized treatment group sequence over time will be provided up to Week 64.

No missing data imputation will be applied. All efficacy analyses will be based on As Observed (AO) analysis.

Table 8 below provides the overview of the long-term efficacy analyses to be performed on different endpoints.

Table 8. Summary of Efficacy Variables and Corresponding Analyses for Long-Term Efficacy Analysis

Efficacy Variables	Analysis Method
Binary Endpoints:	

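### Efficacy at Weeks 36 to 64 is reported As Observed only, and no display shows whose csDMARD or steroid therapy was intensified after the Week 24 adjustment

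*SAP*

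**What the plan says.** **Before Week 24.** Protocol Section 5.2.3.1 allows csDMARD doses only to be lowered, and only for safety. Section 5.2.3.2 bars steroid injections and oral steroids above 10 mg/day prednisone equivalent.

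**At Week 24.** The IRT computes CDAI (Protocol Section 5.3.1.1). If the subject is not in LDA, defined as CDAI of 10 or less, the synopsis says "the investigator should adjust the subject's background RA therapies after assessments for Week 24 have been completed". From then on the plan allows "initiation of or change in corticosteroids, non-steroidal anti-inflammatory drugs (NSAIDs), acetaminophen/paracetamol, low potency analgesics, or csDMARDs". Section 5.2.3.1 also permits steroid injections from this point.

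**Analysis.** SAP Section 9.3 summarises ACR20/50/70, LDA, remission and the continuous measures by randomized sequence up to Week 64: "All efficacy analyses will be based on As Observed (AO) analysis". The AO definition in SAP Section 9.1.2 reads: "Regardless of treatment switching or premature discontinuation of study drug, all observed data will be used in the analysis". It names treatment switching and stopping of study drug, but not a change in background therapy. SAP Section 9.1.1 sets the status of this analysis: "There will be no statistical testing; only descriptive statistics and confidence intervals will be provided".

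**Objective.** For Period 2, SAP Section 4.1 states: "To evaluate the long-term safety, tolerability, and efficacy of upadacitinib 15 mg QD".

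**The concern.** The adjustment is directed by the protocol, happens at a known visit and falls on subjects selected for insufficient response. It follows the Week 24 assessments, so the first scheduled visit that can reflect it is Week 36. From there each sequence combines subjects on upadacitinib with unchanged background and subjects on upadacitinib plus a new or increased csDMARD or steroid, under a label that names upadacitinib 15 mg QD alone.

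A reader who sees LDA or ACR50 rise between Week 24 and Week 48 cannot tell how many of the responders had been intensified. The protocol recognises this kind of confounding elsewhere: Section 5.2.3.1 withholds as-needed analgesics for 24 hours before a visit and asks that joint injections be avoided in the 21 days before one. The SAP has no counterpart for csDMARDs or systemic steroids.

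**Working it through.** **1. What can change after Week 24, and where the plan would show it**

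| Change | Existing provision | What stays hidden |
|---|---|---|
| csDMARD added or increased | Concomitant medication table by generic name (SAP 6.3) | Timing, dose increases, link to response |
| Systemic steroid started in a baseline non-user | Same table | Timing, link to response |
| Steroid dose increased in a baseline user | Proportion with no steroid use, among baseline users (SAP 9.3) | An increase looks the same as unchanged use |
| Intra-articular injection | Joint not assessable for 3 months (Protocol 5.2.3.1, 5.3.1.1); count extrapolated proportionally (SAP 9.4.2) | Number injected; effect outside that joint |

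Protocol Section 5.3.3.2 lists concomitant corticosteroid use, systemic and intra-articular, as a Period 2 measure without restricting it to baseline users. SAP Section 9.3 is narrower.

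**2. The plan's own figure**

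Neither document gives a figure for long-term efficacy. The stated power, over 90% at Week 12 (SAP Section 4.3), reproduces:

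- Inputs: 36.7% versus 36.7 + 21.7 = 58.4%; 161 per arm less 10% = 145; two-sided 0.05.
- Normal approximation with pooled variance under the null: power 96.3%.

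This concerns visits before any adjustment, so the point leaves it unchanged.

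**3. Possible size for LDA (illustration)**

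The documents give no Week 24 CDAI LDA rate and no effect of added therapy. Let *q* be the share not in LDA at Week 24 and *c* the share of these who reach LDA only because of the adjustment. Assume that all of *q* are adjusted, that none of them would reach LDA without it, and that nobody in LDA loses it.

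- AO rate = (1 − q) + q·c
- Composite rate (adjusted subjects counted as non-responders) = 1 − q
- Gap = q·c

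| q | Composite | AO, c = 10% | AO, c = 20% | AO, c = 30% | Gap (points) |
|---|---|---|---|---|---|
| 40% | 60% | 64% | 68% | 72% | 4, 8, 12 |
| 52% | 48% | 53.2% | 58.4% | 63.6% | 5.2, 10.4, 15.6 |
| 60% | 40% | 46% | 52% | 58% | 6, 12, 18 |

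The middle row uses 100 − 48 = 52% not in LDA, from Protocol Table 1. That figure is DAS28(CRP) at Week 12 in the earlier Phase 3 study, so it is only a loose anchor for CDAI at Week 24 here.

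**4. Compared with the interval to be printed**

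The AO 95% CI half-width at 48% with 145 per sequence is 1.96 × √(0.48 × 0.52 / 145) = 8.1 points. The 145 carries the 10% dropout assumption over to later visits. The gap may be smaller or larger than the printed uncertainty, and the interval says nothing about it.

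**The case against.** The strongest reply is that AO answers a legitimate question. Upadacitinib is given on background csDMARDs throughout, optimisation at Week 24 is part of the protocol, and AO describes outcome under that regimen. Period 2 is open-label with no control after Week 12, so no display could isolate the effect of upadacitinib. Nothing is tested, and SAP Section 9.1.1 takes the key efficacy findings from Period 1. All of this stands. It is why AO should remain the main display and why the point concerns reporting. It does not explain why the number intensified should go unseen.

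Four stronger readings are tempting, and the documents do not support them:

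- *Every subject not in LDA is escalated.* The wording is that the investigator should adjust, with changes then allowed under the local label. Uptake is unknown.
- *The plan ignores the issue.* The steroid-free endpoint, the medication table and the injected-joint rule are partial accounts.
- *The late results are a biased estimate of drug effect.* They are uncontrolled descriptions, and both sequences receive upadacitinib by then.
- *The share adjusted multiplied by their later response rate is the effect of the added therapy.* That product is only the gap to a composite. CDAI above 10 is not ACR non-response: a subject can be an ACR20 responder at Week 24 and still be adjusted, and some would have responded anyway.

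One related limit would remain. Subjects without 20% improvement in both joint counts at two consecutive visits from Week 24 must leave (Protocol Section 5.4.1). This removes poor responders from AO denominators and also pushes late rates upward. The display proposed here does not address it.

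**Conclusion.** The point holds as a limit on interpretation. AO results at Weeks 36, 48 and 64 mix stable and intensified background therapy, and nothing planned lets a reader see in what proportion. Week 12 inference, alpha and power are unaffected.

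The size cannot be derived from the documents. The 4 to 18 points for LDA rest wholly on the assumed ranges, 40-60% not in LDA and 10-30% of them converted only by adjustment, and on the simplifications stated with the calculation. The change is worth making because it is cheap and the missing information bears directly on how the Period 2 efficacy objective is read.

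**What to change.** In SAP Section 9.3 and Table 8, keep AO as the main display and add:

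1. **Counts.** By sequence and visit, the number of subjects who after the Week 24 assessment started or increased a csDMARD or a systemic corticosteroid, or had a steroid injection. Include all subjects, not only baseline steroid users.
2. **A supplementary result beside AO at Weeks 36, 48 and 64.** For ACR20/50/70, LDA and remission, count as non-responders, from the change onward, subjects who started or increased a csDMARD or had a sustained start or increase of systemic corticosteroid. Leave out inhaled steroids and the short flare course that the protocol permits; otherwise brief permitted use would become permanent failure. Define "sustained" in the SAP in advance, and use the AO denominator so that the two rates differ only by this rule. For continuous endpoints, show data up to the change.
3. **A label** on late AO tables and plots stating that they include adjusted background therapy.

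The data exist: Protocol Section 5.2.3 records dates, dose, route and frequency for every concomitant medication. The cost is a few more descriptive tables and a lower, conservative second figure beside AO. No clinical rule, sample size or Period 1 analysis changes.
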